- Maintenance of wakefulness test (MWT) mean sleep latency
- Multiple Sleep Latency Test (MSLT) mean sleep latency
- Fatigue Severity Scale (FSS) global score

Adherence

- Rate of patients compliant with their OZAWADE® treatment (according to the 8-item Morisky Score) at each visit.
- Rate of patients compliant with their primary therapy (according to the mean number of hours of
 use per night during the last three months) at each visit.

Other

Incidence of car accidents at driving (comparison of answers to the questionnaire "assessment of sleeping at driving" between inclusion and yearly evaluation)

Study Procedures

During the 2-year enrolment phase, 502 patients are planned to be recruited in four to five countries where OZAWADE® is on the market (*i.e.*, France, Germany, Italy and possibly Netherlands, Belgium or Spain), in approximately 8 to 15 centers per country. In each center, participating physicians will enrol all eligible patients consecutively according to a systematic sampling technique (*i.e.*, in chronological order of their arrival at the consultation) irrespective of the treatment decision (i.e. patients prescribed and not prescribed OZAWADE®) until the recruitment target is reached globally in both groups or until the end of the enrolment period. Patients will be followed-up up to 5 years (follow-up visit at six months and then once a year).

Duration of Study

There will be approximately two years of recruitment and five years of follow-up.

Selection of the Patients

Inclusion Criteria

A patient must meet all of the following criteria to be eligible for participation in the study:

- 1. Patients with OSA, treated or not by primary therapy (e.g., CPAP, MAD).
- 2. Patients eligible for treatment by OZAWADE® as per SmPC (being prescribed or not with OZAWADE®).
- 3. Patients naive of treatment with any wake-promoting agent or patients previously treated with wake-promoting agent for less than six months and having discontinued the treatment for at least three months.
- 4. Patient informed about the study and who either did not oppose to their data collection or who signed the Informed Consent Form when applicable.

Exclusion Criteria

A patient who meets the following criterion is not eligible for participation in the study:

- 1. Patient participating in a clinical trial.
- 2. Patient under curatorship or deprived of liberty.

Variables

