The estimates of the main endpoint will be compared among OZAWADE® users and non-users by a generalized Linear Model featuring Poisson regression. In this model we consider a post stratification model based on fixed covariates combined with a random effect attempting a correction on the expected imbalance due to the non-randomized treatment. Cumulative incidence estimate and Cox proportional Hazard regression will be used as secondary analysis.

Milestones

• Ethics submission: Q2/Q3 2024

Start of data collection: Q3/Q4 2024

• End of data collection: Q4 2030/Q1 2031

• Interim study report: yearly throughout the study

Final report of study results: Q4 2031

5. Amendments and updates

None.

6. Milestones

The planned study milestones, as per Good Pharmacovigilance Practices definitions, are summarized below.

Table 1. Study Milestones

Study Milestone	Planned date
Ethics submission	Q2/Q3 2024
Start of data collection	Q3/Q4 2024
End of data collection	Q4 2030/Q1 2031
Interim study report	Yearly throughout the study
Final report of study results	Q4 2031

7. Rationale and background

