9.1. Study design

9.1.1. Overall Design of the Study

This is a prospective, observational, multi-center, open-label, long term, cohort study (OZAWADE® exposed and OZAWADE® unexposed) designed to collect data on the long-term safety of OZAWADE® treatment. This study will be conducted in OSA patients with EDS whose EDS has not been satisfactorily treated by, or who have not tolerated OSA primary therapy. The study will be conducted by physicians specialized in sleep management such as sleep specialists, pulmonologists, cardiologists, otorhinolaryngologist and neurologists.

[figure not shown]
As an observational study, the assignment of the patient to a particular therapeutic strategy should be decided within the current clinical practice and the decision to prescribe OZAWADE® should necessarily precede and be independent of the decision to enrol the patient into the study. OZAWADE® should be prescribed and used based on the routine clinical practice as well as on the individual situation of each patient, according to the approved SmPC.

During the 2-year enrolment phase, 502 patients are planned to be recruited in four to five countries where OZAWADE® is on the market (*i.e.*, France, Germany, Italy and possibly Netherlands, Belgium or Spain), in approximately 8 to 15 centers per country.

Once eligible patients are enrolled, baseline data should be collected. Data collected in the CRF will correspond to data collected in routine practice in the investigating centers.

Patients will be followed-up up to five years, during which time they should be assessed by their treating participating physicians at 6, 12, 24, 36, 48 and 60 months, to follow routine care schedule.

Study visits, procedure and evaluations are summarized in the study flow (Figure 1) and schedule of assessments below (Table 2).

CPAP: Continuous Positive Airway Pressure; EDS: Excessive Daytime Sleepiness; FU: Follow-up; MAD: Mandibular Advancement Device; OSA: Obstructive Sleep Apnoea.

Figure 1: Study Flow.

PASS Protocol [P21-02/OZAWADE]

OZAWADE

Table 2. Schedule of Assessments

	Procedures ¹ /Visits	Inclusion	FU 6 Months	FU Year 1	FU Year 2	FU Year 3	FU Year 4	FU Year 5	End of study
	Visit window		6M [3-9M[12M [9-18M[24M [18-30M[36M [30-42M[48M [42-54M[60M [54-66M[
	Demography: age, gender	X	ē.						
	Profession / Socio-economic status	Х							
Patient interview	Height², weight	Х	Х	Х	X	X	X	X	Х
nten	Waist circumference	X	х	Х	X	X	X	х	Х

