9.1.2. Primary, secondary and exploratory endpoints

9.1.2.1. Primary endpoint

The primary endpoint will be the occurrence of at least one cardiovascular event (CVE) or one serious drug related adverse event during the five years of follow up for each participating patient.

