9.2.2.2. Patient Enrolment

During the enrolment period, participating physicians will be asked to report in a patient log all eligible patients presenting for consultation. This log will therefore list all eligible patients whether they accept to participate in the study or not. The overall representativeness of the patients enrolled in the study population will be assessed from the data collected in this patient log.

During the 2-year enrolment phase, 502 patients are planned to be recruited in four to five countries where OZAWADE® is available on the market (i.e., France, Germany, Italy and possibly Netherlands, Belgium or Spain), in approximately 8 to 15 centers per country. In each center, participating physicians will enrol all eligible patients consecutively according to a systematic sampling technique (i.e., in chronological order of their arrival at the consultation) irrespective of the treatment decision (i.e. patients prescribed and not prescribed OZAWADE®) until the recruitment target is reached globally in both groups or until the end of the enrolment period.

During the recruitment phase, and for each patient, participating physicians will:

- Explain the study to the patient, in particular, the objective of the study and its observational nature. Indications will be given on the aim and timelines for visits, as per routine clinical practice.
- Give the patient, either the "patient information and non-opposition note" or the "patient information note and Informed Consent Form", where locally applicable, and ask the patient to read it. After sufficient time to consider his/her decision, the patient will confirm (or not) his/her oral agreement (for non-opposition) to participate (which will be also recorded in the patient medical records) or sign (or not) the Informed Consent Form (when locally applicable).
- For patients who agree to participate in the study: give the baseline patient reported outcome (PRO) questionnaires and ask the patient to complete the questionnaires.

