9.9. Limitations of the research methods

The design of this study was carried out in order to limit the major usual biases for this type of study. However, as any observational research this study is subject to risks of bias.

Patient selection bias: selection bias should be taken into account when interpreting the results of the study, especially the limitation on generalizability of study data. It is planned to have a sample of 195 patients exposed to OZAWADE® and 195 not exposed. These results will thus provide a good insight on OZAWADE® data outside the context of an interventional study by providing descriptive data in a real-life context. The

description and follow-up of this subset of patients followed in four countries will be of scientific value. However, to limit selection bias, any physician specialized in sleep medicine who receive, in medical consultation, OSA patients with diagnosis of excessive daytime sleepiness and who are likely to treat them with OZAWADE (sleep specialists, pulmonologists, cardiologists, otorhinolaryngologists and neurologists) will be selected.

Information bias / measurement bias: each subject included in the study has his/her own physician, and therefore, it is expected that information issued from source dossier (i.e. medical file) will be different from a subject to another and may possibly lead to an information and measurement biases. Response and safety assessments may not be uniform. This bias is inherent to the usual physician practice and such study design, and cannot be avoided. To minimize this bias, a training session during on-site study initiation meetings will be provided to all physicians involved in the study, in which clear definitions of the variables measured will be explained.

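### The milestone dates allow about 6.0 to 6.5 years of data collection, but two years of recruitment plus five years of follow-up needs about seven

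*Protocol*

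**What the plan says.** Four statements in the Protocol bear on the calendar.

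- **Milestones** (section 4, Abstract, and again in section 6, Table 1): "Start of data collection: Q3/Q4 2024", "End of data collection: Q4 2030/Q1 2031" and "Final report of study results: Q4 2031".
- **Duration** (section 4, Duration of Study): "There will be approximately two years of recruitment and five years of follow-up". Sections 4, 9.1.1 and 9.2.2.2 also speak of a two-year enrolment phase.
- **Primary endpoint** (section 9.1.2.1): occurrence of an event "during the five years of follow up for each participating patient".
- **Follow-up** (sections 4 and 9.1.1): five years is given as a maximum, with visits to month 60. Table 2 sets the Year 5 window from month 54 to just before month 66.

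The primary model in section 9.7.5 carries the logarithm of exposure duration as an offset.

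**The concern.** The dates and the durations cannot all be true. If data collection closes on the stated date and enrolment takes the stated two years, patients enrolled late are cut off before month 60, and the endpoint as defined is not observable for them. The follow-up lost is all late follow-up. Section 7.2 names long-term safety as the missing information this study was agreed to supply.

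Some summaries are also more exposed than the primary model. Section 9.7.7 computes adverse event incidences with all patients in the denominator, so truncated follow-up lowers those percentages. Section 9.1.2.3 measures effectiveness as change to the end of study, which would fall at different follow-up times for different patients.

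**Working it through.** **Required span.** Two years of recruitment plus five of follow-up gives 2 + 5 = 7 years. Enrolment cannot start before data collection does, because baseline data are taken at inclusion (section 9.1.1).

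**Available span, S**, from the quarter boundaries:

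- Q3 2024 to Q4 2030: from 30 Sep 2024 to 1 Oct 2030 = 6.0 years, up to 1 Jul 2024 to 31 Dec 2030 = 6.5 years.
- Q4 2024 to Q1 2031: from 31 Dec 2024 to 1 Jan 2031 = 6.0 years, up to 1 Oct 2024 to 31 Mar 2031 = 6.5 years.
- Shortest cross-pairing: 31 Dec 2024 to 1 Oct 2030 = 5.75 years.
- Longest cross-pairing: 1 Jul 2024 to 31 Mar 2031 = 6.75 years.

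The shortfall, 7 − S, is 0.5 to 1.0 year with the quarters paired as written and 0.25 to 1.25 years at the extremes.

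**Consequences**, assuming uniform accrual over two years and no dropout:

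- Follow-up available to the last patient = S − 2.
- Share unable to reach month 60 = (7 − S)/2.
- Share unable to reach month 54 = max(0, (6.5 − S)/2).
- Mean person-years lost per patient = (7 − S)/2 × (7 − S)/2 = (7 − S)²/4, divided by 5 for the fraction lost.

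| S (years) | Last patient (years) | Short of month 60 | Of 502 | Short of month 54 | Person-years lost |
|---|---|---|---|---|---|
| 5.75 (extreme) | 3.75 | 62.5% | 314 | 37.5% | 0.391/5 = 7.8% |
| 6.0 | 4.0 | 50% | 251 | 25% | 0.25/5 = 5% |
| 6.5 | 4.5 | 25% | 126 | 0% | 0.0625/5 = 1.25% |
| 6.75 (extreme) | 4.75 | 12.5% | 63 | 0% | 0.0156/5 = 0.3% |

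**Dates that would fit.** A start in Q3/Q4 2024 plus seven years puts the last month-60 point in Q3/Q4 2031. Using the Year 5 window to its end at month 66 adds six months, giving Q1/Q2 2032. The final report is now due in Q4 2031, so it would coincide with or precede the end of data collection.

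**Enrolment that would fit.** If the stated end date stands, every patient can reach month 60 only if enrolment closes within S − 5 = 1.0 to 1.5 years (0.75 to 1.75 at the extremes).

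**The case against.** The Protocol contains several cushions:

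- Recruitment is only approximately two years and may stop sooner, "until the recruitment target is reached globally in both groups or until the end of the enrolment period". This removes the conflict only if accrual finishes in about 1.0 to 1.5 years, which is not what the enrolment sections plan.
- The design sections give five years as a maximum. That wording suits the calendar, but it conflicts with an endpoint defined over five years for each patient.
- The Year 5 window opens at month 54. With a span of 6.5 years or more the last patient can have an in-window visit, though never 60 months of observation.
- The exposure offset and the censoring in the secondary Cox model (section 9.7.6) handle unequal follow-up. This stands. The main rate analyses remain valid, and the person-time lost is modest. The 62.5% and 7.8% figures pair the latest start with the earliest end and should not be read as central values.

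A reader might also infer that the planned size contradicts itself. Section 9.1.1 says "During the 2-year enrolment phase, 502 patients are planned to be recruited", while section 9.9 says "It is planned to have a sample of 195 patients exposed to OZAWADE® and 195 not exposed", which totals 390. From this a reader might expect recruitment to close at 195 per group. The document does not support that reading. The bodies of the sample size sections and of Appendix 1, where recruited and evaluable numbers would be linked, are absent from the public text. Section 9.9 is a discussion of bias and sets no stopping rule. The stopping rule in section 9.2.2.2 sits beside the 502. The ratio 390/502 = 0.777 is compatible with an attrition allowance. For example, an assumed loss hazard of 0.05 per year over five years gives 195/exp(−0.25) = 250.4, hence 251 per group and 502 in total. No visible text states that rate, so this shows only that the two figures can coexist.

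**Conclusion.** The calendar conflict is confirmed on every reading of the quarters. The stated dates fall short of the stated design by 0.5 to 1.0 year (0.25 to 1.25 at the extremes). The shortfall itself is simple date arithmetic. The shares of patients affected (about 25% to 50% short of month 60) and of person-years lost (about 1.25% to 5%) rest on uniform accrual over the full two years and ignore dropout. As written, the primary endpoint cannot be observed over five years for late enrollees.

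The point should be fixed, but it does not undermine the primary rate comparison, which adjusts for exposure time. The difference between 502 and 195 per group is not upheld as an error.

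**What to change.** Choose one of two corrections and apply it in the Abstract and in Table 1:

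1. Move the end of data collection to Q3/Q4 2031 or later (Q1/Q2 2032 if the whole Year 5 window is to be used), and place the final report after it. The cost is a later report.
2. Keep the dates, and restate the follow-up and the primary endpoint in sections 4, 9.1.1 and 9.1.2.1 as at most five years with administrative censoring at the close of data collection. Say that the last enrollees will contribute about 4 to 4.5 years. The cost is a slightly less favourable follow-up statement.

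Both are changes of text. As an optional clarification, section 9.9 could state what 195 per group denotes.

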7.1. Background

Obstructive Sleep Apnoea (OSA) is a highly prevalent chronic disease affecting nearly 1 billion people aged 30–69 years worldwide [1]. OSA is characterized by repetitive collapses of the upper airway during sleep, resulting in intermittent hypoxia, leading to secondary sympathetic activation, oxidative stress and systemic inflammation [2]. The diagnosis of OSA is based on the apnoea-hypopnoea index (AHI) – that is the number of apnoeas and hypopnoeas per hour of sleep, as determined by standard overnight polysomnography –, and the presence of other symptoms such as daytime sleepiness or fatigue [3, 4]. According to the American Academy of Sleep Medicine, OSA is classified as mild with AHI of 5–15, moderate with AHI of 16–30, and severe with AHI > 30 [3]. The mechanisms of OSA are multifactorial, including obesity, craniofacial changes, alteration in upper airway muscle function, and pharyngeal neuropathy [2]. OSA is recognized as associated with poor health outcomes, including cardiovascular diseases (mainly hypertension), diabetes, cognitive deficits and early mortality [2, 5-8].

Excessive daytime sleepiness (EDS) is a prominent symptom of OSA and is associated with a higher incidence of concentration difficulties, impaired vigilance, depressive symptoms, and increased risk of accidents [9, 10]. This impairment in daily functioning and deterioration in quality of life results in considerable economic and societal burdens. EDS has been reported to affect 12 to 58 % of people with OSA [11-13]. The variations in EDS prevalence could be explained by different factors such as the nature of EDS and the variety of factors impacting its presentation, the overlap with other comorbidities and the existence of various tools for EDS assessment. The Epworth Sleepiness Scale (ESS) is the most commonly used self-administered assessment for EDS [14]. The ESS evaluates the propensity to fall asleep in common real-world situations. A cut-off of > 10 points in the ESS is accepted to indicate EDS [15-17].

Continuous positive airway pressure (CPAP) is the gold-standard first-line treatment for patients with symptomatic OSA. CPAP acts as a pneumatic splint to the upper airway during sleep allowing restoration of upper airway patency and thus normalization of oxygen saturation and sleep quality and architecture. CPAP was shown to improve cognitive function and quality of life and to reduce daytime sleepiness in adherent patients [18, 19]. Adherence is one of the major issues with long-term CPAP therapy. A recent study in France showed that the overall rate of CPAP therapy termination was 48 % at 3 years [20]. Also, a substantial proportion of CPAP-treated OSA patients continue to experience EDS despite optimized CPAP therapy. Residual EDS has been reported to affect 6 to 15 % of CPAP-treated (> 3 hours/night) OSA patients [21, 22]. In these patients, for whom other sleep disorders or psychiatric disorders have been ruled out, pharmacologic therapy with wake-promoting agent, for residual EDS is now recommended [17].

Wake-promoting agents, such as modafinil and, more recently, solriamfetol were shown to significantly improve residual EDS in OSA patients treated with CPAP [23-26]. Yet, the European Medicines Agency (EMA) removed the indication for modafinil (and restricted its use to narcolepsy) because of potential cardiovascular safety concerns observed in trials in OSA patients [27]. Solriamfetol has been approved for the treatment of residual EDS in patients with OSA whose EDS has not been satisfactorily treated by primary OSA therapy, in 2019 in the USA and in 2020 in Europe.

Pitolisant is a selective histamine H3 inverse agonist/antagonist. Double-blinded placebo-controlled phase III trials demonstrated pitolisant strong wake-promoting effects and safety profile in patients with narcolepsy [28-30]. Pitolisant, under the trade name of Wakix®, has been authorized for use in the EU in this indication, in adults and children, on March 31, 2016 and in the USA in adults, in 2019. Efficacy of pitolisant was also demonstrated during double-blinded placebo-controlled phase III trials in OSA patients treated or not with

CPAP. In OSA patients with residual EDS, refusing or non-adherent to CPAP, pitolisant significantly reduced self-reported daytime sleepiness and fatigue, and improved patient-reported outcomes and physician disease severity assessment after 12 weeks of treatment [31]. Pitolisant, used as adjunct to CPAP therapy for OSA with residual EDS despite good CPAP adherence, also significantly reduced subjective and objective sleepiness and improved participant-reported outcomes and physician-reported disease severity after 12 weeks [32]. In two dedicated QT studies, supra-therapeutic doses of pitolisant (6-12-times the therapeutic dose, that is 108 mg to 216 mg) produced mild to moderate prolongation of QTc interval (10-13 ms). As reported in the OZAWADE® SmPC, patients with cardiac disease, hypertension, at risk of major adverse cardiovascular events (MACE), co-medicated with other QT-prolonging medicinal products or known to increase the risk of repolarization disorders, or co-medicated with medicinal products that significantly increase pitolisant Cmax and AUC ratio or patients with severe renal or moderate hepatic impairment should be carefully monitored [33].

Clinical studies have not raised any safety concerns and confirmed in OSA patients the favourable safety profile of pitolisant as reported in patients with narcolepsy. Pitolisant, under the trade name OZAWADE®, has been authorized for use in the EU on July 22, 2021, to improve wakefulness and reduce EDS in adult patients with OSA whose EDS has not been satisfactorily treated by, or who have not tolerated OSA primary therapy, such as CPAP.

7.2. Rationale

The Risk Management Plan for OZAWADE® identifies some potential risks and missing information about safety. One of the potential risks concerns cardiovascular (CV) events including QT-interval prolongation and the missing information refers to the long-term safety of OSA patient treated with OZAWADE®, according to the SmPC.

The Sponsor has agreed with the EMA to conduct a Post-Authorization Safety Study (PASS) as part of the Risk Management Plan (RMP) for OZAWADE®.

8. Research question and objectives

8.1. Primary objective

The primary objective of this study is to demonstrate that OZAWADE® supplementation in obstructive sleep apnoea (OSA) patients does not increase the incidence of cardiovascular events (CVE) compared with OZAWADE® unexposed patients (non-inferiority) and to evaluate the long-term safety of OZAWADE® when used as per SmPC in patients with OSA.

